## **11.4 Analysis Methods**

### **11.4.1 Timing of Analysis**

Final analysis will occur after all subjects have completed their Final visit or otherwise have come off study.

### **11.4.2 Subject Disposition**

A summary of all consenting subjects will be provided at the end of the study. This will include those that consented, enrolled, screen failed, died, were lost to follow-up or withdrew consent.

### **11.4.3 Baseline Subject Characteristics**

A summary of subject demographics will be completed.

### **11.4.4 Primary Analysis**

The proportion (the denominator being the number of evaluable subjects) of evaluable subjects undergoing PGx testing and receiving at least one drug/dose selection/modification based on their test results at any study visit where PGx results are available will be calculated, alongside 95% Clopper-Pearson confidence intervals.

### 11.4.5 Secondary Analysis

Total counts and descriptive statistics of the number of drug/dose selection/modifications made due to subject PGx test results at all visits where PGx results are available will be summarized.

A single-arm analysis for the PGx cohort will be performed: Descriptive statistics of ESAS pain scores and PHQ-9 depression scores will be calculated and summarized at study visits. Repeated-measures linear mixed models will be estimated for pain and depression, separately, adjusted for baseline clinicodemographic characteristics and include a main effect for time and a random effect for subject.

The following analysis will be performed for both the PGx and control cohorts:

A matched analysis for ESAS pain and depression scores will be carried out, comparing the study cohort to a matched cohort of unique patients receiving clinical management alone during the same time period the trial is enrolling. Standard-of-care patients with ESAS pain  $\geq 4$  and/or depression scores  $\geq 3$  at their first visit to the palliative medicine clinic or a re-establishment of care visit with the last visit being at least 1 year prior—these visits occurring within the same time period the trial is enrolling—will be identified and considered in the matched analysis.

Enrolled subjects will be matched to a similar case in cohort by:

- ESAS pain and depression symptom scores at first visit to palliative medicine clinic (i.e., study screening for study cohort)
- Age
- Sex
- Race
- Clinic visit schedule.

Between-group comparisons of those study subjects and control patients will be performed estimating repeated-measures linear mixed models for pain and depression, separately, to estimate the effect of PGx testing (i.e., treatment effect) on symptom scores adjusted for baseline clinicodemographic characteristics, a main effect for treatment, for time, an effect for treatment by time interaction, and a random effect for subject.

Additionally, the average post-baseline symptom score will be calculated for each individual (separately for pain and depression). The distributions of the average post-baseline symptom scores will be compared between the cohorts using analysis of variance techniques with adjustments for clinicodemographic characteristics.

Health care utilization (e.g., instances of participant presenting at an emergency department, admitted as an inpatient, any outpatient encounter, or medication prescription) and reason for encounter will be assessed during the study period (starting on the Baseline to the Final study visit) for those undergoing PGx testing. HCRU in year prior to start of study enrollment will be collected for patients from institutional enterprise data warehouse (EDW) via raw billing and medical record data. Insurance status and/or type at each encounter will also be collected. An encounter resulting from another (e.g., ED presentation leading to IP) will be counted separately. Any ED encounter lasting longer than 24 hours will be considered an IP encounter. Diagnosis and procedure codes and priority sequence numbers will be collected from the EDW at least 6 months following study closure to allow for final bills to accrue for HCRU encounters, for those that underwent PGx testing and matched controls. Diagnosis and procedure codes used in billing for each encounter will be used to estimate institutional costs or reimbursement and/or to publicly available sources (e.g., CMS fee schedule) and to obtain patient's historical prescription drugs. Endpoints will be summarized by encounter-level and patient-level data files for frequency of HCRU and descriptive analysis of associated cost. Once data files have been constructed, data will be fit to appropriate statistical analyses and multivariate regression will be employed to interrogate the relationship between costs, resource utilization PGx results, sociodemographic, and clinical patient characteristics. Sensitivity and scenario analyses will be conducted to assess the robustness of model estimates.

Subject responses to survey tool administered at the Final visit (or sooner if withdrawn) will be summarized and described. Regression models may be estimated to describe the association of response and responder characteristic, both univariately and multivariately, adjusted for relevant baseline characteristics.

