#### **2.1.2 Secondary Objectives**

- Determine the impact of PGx on treatment outcomes by measuring pain scores using the Edmonton Symptom Assessment Scale (ESAS) ([Appendix A](#)) and depression scores using the Patient Health Questionnaire (PHQ) 9 ([Appendix B](#)) at study visits after the Baseline study visit. Symptom scores will also be compared between those receiving PGx testing and a matched control receiving clinical management alone.
- Describe subject perspectives ([Appendix C](#)) of PGx testing using a survey administered to subjects after/at the Final visit (or sooner if withdrawn).

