## **11.2 Sample Size and Accrual**

Enrollment to the study will continue until 65 evaluable subjects have been identified ([Section 11.3](#)).

We anticipate enrolling 80 eligible subjects, of which we estimate 65 will be evaluable (defined in [11.3](#)). With this sample size, the width of the 95% Clopper-Pearson confidence interval will be  $\leq 25\%$ , regardless of the observed DDSM rate.

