## **11.3 Analysis Populations**

Analyses of the primary objectives and secondary objectives concerning counts of PGx-guided drug/dose selections or modifications based on their test results will be conducted on the evaluable population, defined as the population of enrolled subjects with confirmed malignancy (per provider documentation) and completing at least one study visit where PGx results are available (including the baseline visit).

Analyses of secondary objectives concerning the impact of PGx on pain and depression scores will be conducted on the primary evaluable population with valid pain and/or depression scores for at least one post-Baseline Study visit.

Analyses of secondary objectives concerning health care utilizations, costs, and subject survey responses and all exploratory objectives will be conducted on all enrolled subjects.

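### Controls are matched to all enrolled subjects, but symptoms are analysed in a smaller set, and no rule covers controls whose partner is not analysed

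*Combined protocol and SAP*

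**What the plan says.** Section 2.1.2 makes the comparison with "a matched control receiving clinical management alone" part of a secondary objective. Section 11.4.5 describes it as "comparing the study cohort to a matched cohort of unique patients receiving clinical management alone during the same time period the trial is enrolling". The matching sentence there reads "Enrolled subjects will be matched to a similar case in cohort by" and lists first-visit ESAS pain and depression, age, sex, race and clinic visit schedule.

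Section 11.3 uses a narrower population. The pain and depression analyses are "conducted on the primary evaluable population with valid pain and/or depression scores for at least one post-Baseline Study visit". Evaluable means confirmed malignancy and at least one visit with PGx results in hand, and the Baseline visit alone is enough. Section 11.2 gives the expected numbers: "We anticipate enrolling 80 eligible subjects, of which we estimate 65 will be evaluable".

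The mixed model in Section 11.4.5 has a random effect for subject and no term for the matched pair or set. The documents do not state a numerical ratio, a matching algorithm or caliper, when matching is done, the size of the control pool, a follow-up score requirement for controls, or what happens to a control whose PGx partner is not analysed.

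**The concern.** Matching balances two groups only if both members of each matched set are analysed. Here the set to be matched is larger than the set to be analysed. If the sections are followed as written, controls chosen to resemble PGx subjects who later leave the analysis can remain, with nobody on the PGx side to balance them. The two groups may then differ at first visit on the very scores used for matching. A difference in later scores could partly reflect who stayed in the analysis.

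This is the plan's only controlled comparison of symptoms. The ratio of controls to subjects is a second, separate matter. The PGx side is limited to about 65, whereas controls come from routine records, so the ratio is a part of precision that can be changed without new enrolment.

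**Working it through.** **Inputs.** Enrolled 80 and evaluable 65 (Section 11.2). Symptom set at most about 65 (Section 11.3). One control per subject is the natural reading of the singular wording in Sections 2.1.2 and 11.4.5, but no ratio is stated. Assumed: equal variances, independent subjects, and a first-visit difference d of 1 to 2 points for unpartnered controls. The SD cancels from the ratios below.

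**The plan's own figures.** 65/80 = 0.8125, so 15/80 = 18.75% are not evaluable, and 65/(1 − 0.1875) = 80 reproduces the enrolment figure. The only precision statement is the Clopper-Pearson width for the primary proportion. Its maximum at n = 65 is 25.3%, which agrees with the stated 25% after rounding. No precision figure is given for the matched comparison.

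**Unpartnered controls.** 80 − 65 = 15, or 15/80 = 18.75%. This is a minimum under the plan's own estimate, because a subject with only a Baseline visit is evaluable but has no post-Baseline score.

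**Possible imbalance.** If 65 controls have first-visit mean m and 15 have mean m + d, the mean of all 80 is m + d × 15/80.
- d = 1: shift 0.1875, about 0.19 points
- d = 2: shift 0.375, about 0.38 points

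These are unadjusted first-visit shifts, not bias in the treatment effect.

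**Precision and which subjects are matched.** SE in SD units = sqrt(1/n_PGx + 1/n_control).
- 65 v 65: sqrt(1/65 + 1/65) = 0.1754
- 65 v 80 (all controls kept): sqrt(1/65 + 1/80) = 0.1670, which is 4.8% lower

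Keeping the unpartnered controls therefore costs no precision. The problem is comparability.

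**Precision and the ratio.** With k controls for each of 65 analysed subjects, SE = sqrt((1 + 1/k)/65), and the reduction relative to 1:1 is 1 − sqrt((1 + 1/k)/2).
- 1:2 (130 controls): 0.1519, 13.4% lower
- 1:3 (195 controls): 0.1432, 18.4% lower
- 1:4 (260 controls): 0.1387, 20.9% lower
- no limit on controls: 1 − 1/sqrt(2) = 29.3% lower

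Measured against 65 v 80 instead of 65 v 65, the 1:3 gain is about 14%. If sets have different numbers of controls and each set counts once, 1/k is replaced by its average over sets, so the gain is below the 1:3 figure whenever some subjects have fewer than three.

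**The case against.** The strongest reply is that the plan never says matching comes before exclusions, nor that controls of unanalysed subjects are kept. Some text suggests later matching. Clinic visit schedule is a matching variable, the final analysis waits until all subjects have finished (Section 11.4.1), and billing codes for matched controls are drawn at least six months after study closure. A statistician might restrict to analysed subjects without being told to. That stands as a limit on the claim: this is a mismatch of populations and a missing rule, not a stated decision to keep unpartnered controls.

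A reader might infer that the plan is biased in favour of PGx, because those who leave are sicker. The documents do not support this. Death and inability to attend visits (Section 3.4), or being too ill to complete a questionnaire (Section 5.1.3), relate to illness. A tumour found to be benign (Section 8.1), non-viable swabs (Sections 3.4 and 8.1), or more than 8 weeks to Baseline (Section 3.4) need not. Covariate adjustment would reduce an imbalance, although the plan does not say whether first-visit scores are among the covariates. Controls with no follow-up score also drop out of the analysis of average post-baseline scores, so not all 15 need remain there.

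A reader might also infer that matching all enrolled subjects gives up about 18% of the standard error. It does not. That figure belongs only to 1:3 against 1:1, and the 195 suitable, distinct controls it needs come from a pool of unstated size. One-to-one matching is conventional and not an error, and no precision target is set for this comparison.

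**Conclusion.** The concern holds as a gap between Sections 11.4.5 and 11.3. On the plan's own numbers and a 1:1 reading, at least 15 of 80 matched controls (19%) could have no analysed partner, and nothing in the text or the model deals with them. Balance from matching is therefore not assured. The shift of 0.19 to 0.38 points rests on an assumed 1 to 2 point difference and would be smaller after adjustment. Its direction is unknown.

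The ratio is a separate opportunity to gain precision: up to about 13% at 1:2 or 18% at 1:3, assuming equal variances and independence, and zero if only 1:1 is feasible. The primary endpoint is not affected. The point is worth settling before the controls are selected.

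**What to change.** Amend Section 11.4.5 as follows.

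1. For the symptom comparison, match the PGx subjects in the Section 11.3 symptom analysis set. Alternatively, match all enrolled subjects and drop the whole matched set from the symptom analysis when its PGx member is not analysed. The second option fits the utilization analyses, which Section 11.3 places on all enrolled subjects.
2. Require controls to have at least one post-baseline score in the same time window. Controls have no Baseline study visit, so state how the window is counted from their first palliative medicine visit. Without this rule, PGx subjects are selected for having follow-up and controls are not, even if step 1 is done.
3. State the ratio and a fixed caliper on first-visit pain and depression. Take up to three controls per PGx subject, fewer where close matches run out, and weight controls so that each set counts once.
4. Report the pool size, the number of controls per set and the first-visit balance in the analysed sets.

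The cost is SAP wording and a larger record extraction, with no new enrolment. The downside is that second and third matches will be slightly less close, which the caliper limits.

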## 6. STUDY CALENDAR

### 6.1 Table 2. Study Procedures and assessments

Study Procedures	Registration	Baseline 	Study Visits 	Final Visit 
Informed Consent	X			
Subject demographics 		X		X
Buccal swab collection for genotyping	X 			
Medical/treatment history 		X		
Drug allergies 		X	X	X
PHQ9 		X	X	X
ESAS 	X 	X	X	X
Medication list 		Continuously throughout the study from the Baseline to the Final visit		
Document use of PGx test results 				
Document use of healthcare resource utilization (HCRU) 				
Final visit survey 				X

The Baseline study visit should be completed no earlier than 2 weeks and no later than 8 weeks from the first ESAS completion.

A total of 3 subsequent study visits will occur every 4 weeks ( $\pm$  1 week) after the Baseline visit. The Final study visit will occur 4 weeks ( $\pm$  1 week) after the third completed Study Visit. Subjects will be offered the option to complete study assessments during a clinic visit (in person or virtually) or over the phone.

All the study visits and assessments (including the Baseline visit) can occur during a clinic visit (in-person or utilizing virtual care) or over the phone. Study visits/assessments may be performed by a trained and delegated provider, RN, research coordinator or Pharm D.

Demographics collected during the Baseline visit will be race, ethnicity, insurance status, and zip code. Demographics collected on the Final visit will be annual household income and education level.

Buccal swab collection (Enrollment day) should be performed no later than one week prior to the Baseline study visit (second palliative medicine visit) at the clinic or the subject's home. The specimen may be obtained the same day after the informed consent is signed.

Medical/treatment history: cancer type, stage of disease, ECOG performance status, active chemotherapy, surgery, and radiation therapy within 30 days of the Baseline visit.

Only to medications listed in [Appendix D](#)

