## 7.4 Final Visit

- The Final study visit will occur 4 weeks ( $\pm$  1 week) after the third completed Study Visit.
  - Drug allergies to medications listed in [Appendix D](#)
  - ESAS [Appendix A](#) collected as a SOC
  - PHQ9 [Appendix B](#) collected preferably electronically within 2 business days prior to the study visit, alternatively via paper during a clinic visit or by phone call within 2 business days prior to the study visit
  - Addition or change in medications listed in [Appendix D](#) and/or dosages, and other drugs and/or drug modifications recommended by the pharmacist or provider based on PGx test results outside those in [Appendix D](#)
  - Use of PGx to guide/modify pharmacotherapy regimen
  - HCRU
  - Patient survey ([Appendix C](#))
  - Subject demographics (part of the final survey): annual household income and education level.

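### Both symptom models name a subject effect as their only within-subject term; read as a random intercept, this can understate the standard error of time-trend and treatment-by-time effects

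*Combined protocol and SAP*

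**What the plan says.** Section 11.4.5 defines two symptom analyses. The single-arm model for the PGx cohort adjusts for baseline characteristics and is to "include a main effect for time and a random effect for subject". The matched comparison proceeds by "estimating repeated-measures linear mixed models for pain and depression, separately", with treatment, time, "an effect for treatment by time interaction, and a random effect for subject". Nothing else about within-subject dependence appears in the protocol. It gives no random slope, residual covariance, robust standard error or degrees-of-freedom method, and it does not say whether time is linear or by visit.

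The schedule for PGx subjects is Baseline, then "A total of 3 subsequent study visits will occur every 4 weeks" (section 6.1, Table 2). After the third of these, "The Final study visit will occur 4 weeks" later (section 7.4). That makes five assessments over a nominal 16 weeks, or 12 to 20 weeks if every ±1-week window is used to its limit (4 × 3 to 4 × 5). Controls have no protocol visits; clinic visit schedule is only one of the matching factors.

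Section 11.4.5 also plans a comparison of each person's average post-baseline score.

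**The concern.** A lone subject effect, fitted as a random intercept with independent residuals, is compound symmetry: two scores 4 weeks apart correlate exactly as strongly as two scores 16 weeks apart, and the variance is the same at every visit. The plan does not defend that assumption. Section 1.1 itself describes wide differences between patients in response to supportive care drugs, which makes a common trajectory hard to assume.

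If the assumption fails through decaying correlation or differing slopes, the model puts too little variance on change over time. Time and treatment-by-time are the terms the plan names for the secondary objective on symptom outcomes (section 2.1.2). Intervals for a PGx effect that grows over follow-up could then be too narrow, and a symptom benefit could be claimed too readily.

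**Working it through.** The plan gives no SD, correlation, alpha or power for these models, so there is no stated figure to reproduce. The width bound in section 11.2 concerns the primary proportion and is not an input here.

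**Inputs from the documents.** Five visits four weeks apart (sections 6.1 and 7.4). Cohort size: "We anticipate enrolling 80 eligible subjects, of which we estimate 65 will be evaluable" (section 11.2). Symptom analysis population: "primary evaluable population with valid pain and/or depression scores for at least one post-Baseline Study visit" (section 11.3).

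**Assumptions.** Complete, balanced data on the same five occasions in both cohorts; 1:1 matching, 65 per cohort (no ratio is stated); two-sided 5%; large-sample normal tests. The SE ratios below do not depend on the cohort size.

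**Formula.** Let Σ be the true 5 × 5 within-subject covariance and c a contrast over visits that sums to zero.
- Residual variance that the random-intercept model estimates: W = [trace(Σ) − (sum of all entries of Σ)/5]/4.
- Model variance per subject: W·c′c. True variance per subject: V = c′Σc.
- SE ratio r = √(W·c′c / V). Actual type I error = 2Φ(−1.96 r).

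The single-arm time effect has the same r, because the two-cohort factor cancels.

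**Linear time**, c = (−2, −1, 0, 1, 2), c′c = 10.

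*Pure AR(1), unit variance, 4-week correlation 0.5.* The entries of Σ sum to 5 + 2(4×0.5 + 3×0.25 + 2×0.125 + 0.0625) = 11.125. W = (5 − 2.225)/4 = 0.694. V = 10 + 2(4×0.5 − 1×0.25 − 4×0.125 − 4×0.0625) = 12. So r = √(6.94/12) = 0.76 and type I error is 13.6%. Over 16 weeks the model SE is 4·√(2/65)·√(0.694/10) = 0.185 SD, against a true 4·√(2/65)·√12/10 = 0.243 SD. Correlations of 0.6 and 0.7 give r = 0.73 and 0.69, and type I errors of 15.5% and 17.3%.

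*Random slopes, total SD 2.5, ICC 0.6, slope SD b points per visit.* Residual variance is 6.25 × 0.4 = 2.5, so W = 2.5 + 2.5b², V = 25 + 100b² and r = √[(1 + b²)/(1 + 4b²)].

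| b | r | Type I error |
|---|---|---|
| 0.2 | 0.947 | 6.3% |
| 0.3 | 0.895 | 7.9% |
| 0.4 | 0.841 | 9.9% |
| 0.5 | 0.791 | 12.1% |

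*Stable subject effect + AR(1) + noise, as variance shares.* The stable part drops out of W and V.
- Shares 0.5/0.2/0.3, AR(1) 0.5: W = 0.2×0.694 + 0.3 = 0.439; V = 0.2×12 + 0.3×10 = 5.4; r = 0.90; type I error 7.7%.
- Shares 0.4/0.4/0.2, AR(1) 0.7 (pure AR(1) values W = 0.480, V = 9.955): W = 0.392; V = 5.98; r = 0.81; type I error 11.3%.

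**Time by visit, pure AR(1) 0.5 to 0.7.**
- Final versus Baseline: r = √[W/(1 − ρ⁴)] = 0.86 to 0.80; type I error 9.2% to 11.9%.
- Week 4 versus Baseline: r = √[W/(1 − ρ)] = 1.18 to 1.27; type I error 2.1% to 1.3%. Here the SE is too large.
- Omnibus 4-df interaction: 6.1% to 7.9% over AR(1) 0.5 to 0.9.
- Effect averaged over all five visits: r = 1.00.

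**Simulation checks.** With 6,000 replicates per scenario and 65 per cohort, the linear test rejected 12.9%, 16.4% and 18.0% under AR(1) 0.5, 0.6 and 0.7, and 6.2% to 11.6% under the four slope SDs. A subject-level slope analysis stayed at 4.4% to 5.2%. In a smaller run of 200 trials at AR(1) 0.7, adding a random slope took rejection from 17.5% to 4.0%; some mixed-model fits in that run gave convergence warnings.

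**The case against.** The text does not say intercept, only or independent residuals, and a repeated-measures mixed model can carry a residual covariance beside a subject effect. That stands as a point about wording: the structure is left open rather than declared. It does not remove the need to settle it, since an analyst following the text literally would fit a random intercept.

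A reader might infer that every standard error is too small unless correlation is constant. The documents do not support that. The direction depends on the contrast and on a coding of time that is not stated: the week-4 contrast is conservative in the same scenarios, and the omnibus test is only mildly inflated. Nor is constant correlation enough, because the model needs equal variance of visit differences.

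A reader might also infer that a false claim of benefit becomes two to three times as likely. That holds only for a linear trend with serial correlation or large slopes. With slope SD 0.2 the excess is about one percentage point, and the highest figures assume pure AR(1) without measurement noise.

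It is also fair that the primary analysis (section 11.4.4) does not use these models, that no decision rule attaches to them, and that the average post-baseline comparison takes one value per person and so does not depend on this assumption. These points limit the stakes; they do not repair the time and treatment-by-time inferences.

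**Conclusion.** The point holds in limited form. As written, both models rest on equal variance and equal correlation across visits 4 to 16 weeks apart. If correlation decays or slopes differ, a linear time or treatment-by-time SE, and late-versus-Baseline contrasts, are understated. For the linear test the type I error is about 6–12% (slope SD 0.2–0.5 points per visit), 8–11% (mixed structures) or 14–17% (pure AR(1) 0.5–0.7). Final versus Baseline by visit is 9–12% under that AR(1).

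Every covariance here is assumed, as are balanced data, and controls seen on clinic schedules will not match that layout. The true size is therefore unknown. The effect is confined to secondary analyses, and the case for a change is that it is cheap.

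**What to change.** In section 11.4.5, for both the single-arm and matched models:

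1. State whether time is linear (and in what unit) or by visit.
2. Replace the single subject effect with a random intercept and slope for subject, or add a residual correlation that decays with the actual time between visits.
3. Report subject-level cluster-robust standard errors with a small-sample correction.
4. Reserve an unstructured covariance for scores on common scheduled visits, such as the PGx single-arm model. It suits the matched model poorly because controls attend on clinic rather than protocol dates.

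The change takes a sentence or two and needs no new data. The price is slightly wider intervals and a few more variance parameters.
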